9.2 Metformin

Metformin will not be supplied by Novo Nordisk.

9.3 Labelling

The trial products will be labelled in accordance with Annex 13²³, local regulations and trial requirements.

Each trial site will be supplied with sufficient trial products for the trial on an on-going basis controlled by the IWRS. Dispensing unit numbers (DUNS) will be distributed to the trial sites according to screening and randomisation.

The investigator must document that direction for use (DFU) is given to the subject orally and in writing at the first dispensing visit (V2). At subsequent dispensing visits it is up to the investigator to assess if it is needed to hand out the DFU as indicated in the flow chart, see section 2).

9.4 Storage

Table 9–2 Storage conditions

Trial product	Storage conditions (not-in-use)	In-use conditions	In-use time*
Insulin degludec/ liraglutide	Store in a refrigerator (2°C – 8°C) Do not freeze Protect from light	Do not store above 30°C Do not freeze Protect from light	Use within 3 weeks
Insulin degludec			

*In-use time starts when the first dose is taken or product is taken out of the refrigerator at subject's residence

The investigator, the head of the study site or the trial product storage manager (if assigned by the head of the study site) must ensure the availability of proper storage conditions, and also record and evaluate the temperature. The investigator must inform Novo Nordisk **immediately** if any trial product has been stored outside specified conditions (e.g. outside temperature range). A temperature log must be kept to document storage within the right temperature interval and storage facilities should be checked frequently. Additional details regarding handling of temperature deviations can be found in the TMM.

Trial product that has been stored improperly must not be dispensed to any subject before it has been evaluated and approved for further use by Novo Nordisk. The investigator must take appropriate action to ensure correct storage.

9.5 Drug accountability and destruction

Drug accountability of all trial products received at site is the responsibility of the investigator.

Returned trial product (used/partly used and unused), expired and damaged trial product can be stored at room temperature and must be stored separately from non-allocated trial product.

Non-allocated trial products including expired or damaged products must be accounted as unused at the latest at closure of the trial site.

The trial products must be accounted for at pen level and either recorded as used/partly used, unused or lost. Returned pens must be sent for destruction, thus may not be re-allocated to new subjects.

Destruction of trial products can be performed on an on-going basis and will be done according to local procedures after accountability is finalised and reconciled by the monitor. Destruction of products must be documented in the IWRS.

9.6 Auxiliary supplies

The following will be provided by Novo Nordisk in accordance with and specified in the TMM:

- DFU for the PDS290 pen injector
- Needles (no longer than 8 mm) for the PDS290 pen injector
- BG meters and BG meter auxiliaries
- Glucose for treating a hypoglycaemia

Only needles provided by Novo Nordisk must be used for administration of trial product.

10 Interactive web response system

A trial-specific IWRS will be set up which can be accessed at any time via the internet or telephone. Access to the IWRS must be restricted to and controlled by authorised persons.

IWRS is used for:

- Screening
- Screening failure
- Randomisation
- Stratification
- Medication arrival
- Dispensing
- Withdrawal
- Completion
- Code break
- Drug accountability
- Data change

IWRS user manuals will be provided to each trial site.

It is important that only DUNs allocated by the IWRS are dispensed to the subject. By doing this it will ensure that;

- The right trial product is dispensed to the right subject
- Needed stock is available at a site for the subjects
- Drug accountability can be made in the IWRS

If a subject requires additional trial product between dispensing visits, the site must perform an additional dispensing session in IWRS.

11 Randomisation procedure and breaking of blinded codes

11.1 Randomisation

Eligible screened subjects will be randomised via the IWRS into two treatment arms in a 1:1 manner.

11.2 Stratification

To ensure an even proportion of subjects on pre-trial basal or pre-mix/combo insulin in each treatment arm, the randomisation will be stratified as in the following with regards to these two different pre-trial insulin therapies combined with metformin with or without one other OAD:

- metformin + basal insulin
- metformin + basal insulin + one other OAD
- metformin + pre-mix/combo insulin
- metformin + pre-mix/combo insulin + one other OAD

11.3 Breaking of blinded codes

The IWRS will notify Novo Nordisk (monitor and the Global Safety department) immediately after the code is broken.

The code for a particular subject may be broken in a medical emergency if knowing the actual treatment would influence the treatment of the subject. Whenever a code is broken the person breaking the code must print the Code Break Confirmation Notification generated by the IWRS, record the reason, and sign and date the document.

When the code is broken, the treatment allocation will be accessible to the investigator and the Novo Nordisk Global Safety department. If IWRS is not accessible at the time of code break the IWRS helpdesk should be contacted. Contact details are listed in [Attachment I](#).

If the code has been broken, the subject must be withdrawn and a withdrawal session must be completed in IWRS.

12 Adverse events, technical complaints and pregnancies

12.1 Definitions

12.1.1 Adverse event

An AE is any untoward medical occurrence in a subject administered a medicinal product, and which does not necessarily have a causal relationship with this treatment.

An AE can therefore be any unfavourable and unintended sign (including an abnormal laboratory finding), symptom or disease temporally associated with the use of a product, whether or not considered related to the product.

An AE includes:

- A clinically significant worsening of a concomitant illness.
- A CLAE: a clinical laboratory abnormality which is clinically significant, i.e. an abnormality that suggests a disease and/or organ toxicity and is of a severity that requires active management. Active management includes active treatment or further investigations, for example change of medicine dose or more frequent follow-up due to the abnormality.

The following should **not** be reported as AEs:

- Pre-existing conditions, including those found as a result of screening or other trial procedures performed before exposure to trial product (pre-existing conditions should be reported as medical history or concomitant illness).
- Pre-planned procedures unless the condition for which the procedure was planned has worsened from the first trial-related activity after the subject has signed the informed consent.
- Non-serious hypoglycaemia is an AE, but is reported on a hypoglycaemic episode form instead of on an AE form, see section [8.5.7](#).

The following three definitions are used when assessing an AE:

- **Severity**
 - **Mild** – no or transient symptoms, no interference with the subject’s daily activities.
 - **Moderate** – marked symptoms, moderate interference with the subject’s daily activities.
 - **Severe** – considerable interference with the subject’s daily activities; unacceptable.
- **Causality**

Relationship between an AE and the relevant trial product(s):

 - **Probable** - Good reason and sufficient documentation to assume a causal relationship.
 - **Possible** - A causal relationship is conceivable and cannot be dismissed.
 - **Unlikely** - The event is most likely related to aetiology other than the trial product.

- **Final outcome**

- **Recovered/resolved** - The subject has fully recovered, or by medical or surgical treatment the condition has returned to the level observed at the first trial-related activity after the subject signed the informed consent.
- **Recovering/resolving** - The condition is improving and the subject is expected to recover from the event. This term is only applicable if the subject has completed the trial or has died from another AE.
- **Recovered/resolved with sequelae** - The subject has recovered from the condition, but with lasting effect due to a disease, injury, treatment or procedure. If a sequela meets an SAE criterion, the AE must be reported as an SAE.
- **Not recovered/not resolved** - The condition of the subject has not improved and the symptoms are unchanged, or the outcome is not known.
- **Fatal** - This term is only applicable if the subject died from a condition related to the reported AE. Outcomes of other reported AEs in a subject before he/she died should be assessed as “recovered/resolved”, “recovering/resolving”, “recovered/resolved with sequelae” or “not recovered/not resolved”. An AE with fatal outcome must be reported as an SAE.
- **Unknown** - This term is only applicable if the subject is lost to follow-up.

12.1.2 Serious adverse event

A SAE is an experience that at any dose results in any of the following:

- Death.
- A life-threatening^a experience.
- In-patient hospitalisation^b or prolongation of existing hospitalisation.
- A persistent or significant disability or incapacity^c.
- A congenital anomaly or birth defect.
- Important medical events that may not result in death, be life threatening^a or require hospitalisation^b may be considered an SAE when - based on appropriate medical judgement - they may jeopardise the subject and may require medical or surgical intervention to prevent one of the outcomes listed in the definition of SAE^d.

^a The term “life threatening” in the definition of SAE refers to an event in which the subject was at risk of death at the time of the event. It does not refer to an event which hypothetically might have caused death if it was more severe.

^b The term “hospitalisation” is used when a subject:

- Is admitted to a hospital or in-patient, irrespective of the duration of physical stay, or
- Stays at the hospital for treatment or observation for more than 24 hours

Medical judgement must always be exercised, and when in doubt, the hospital contact should be regarded as a hospitalisation. Hospitalisations for administrative, trial-related and social purposes do not constitute AEs and should therefore not be reported as AEs or SAEs. Hospital admissions for surgical procedures, planned before trial inclusion, are not considered AEs or SAEs.

^c A substantial disruption of a subject's ability to conduct normal life functions (e.g. following the event or clinical investigation the subject has significant, persistent or permanent change, impairment, damage or disruption in his/her body function or structure, physical activity and/or quality of life).

^d For example intensive treatment in an emergency room or at home of allergic bronchospasm, blood dyscrasia or convulsions that do not result in hospitalisation or development of drug dependency or drug abuse.

The following AEs must always be reported as an SAE using the important medical event criterion if no other seriousness criteria are applicable:

- Suspicion of transmission of infectious agents via the trial product
- Risk of liver injury defined as ALT or AST > 3 x UNL and total bilirubin > 2 x UNL, where no alternative aetiology exists (Hy's law).

12.1.3 Non-serious adverse event

A non-serious AE is any AE which does not fulfil the definition of an SAE.

12.1.4 Medication errors

A medication error concerning trial products is defined as:

- Administration of wrong drug or use of wrong device.
- Use of wrong DUN is not considered a medication error.
- Wrong route of administration, such as intramuscular instead of subcutaneous
- Administration of an overdose with the intention to cause harm (e.g. suicide attempt), misuse or abuse of trial product.
- Accidental administration of a lower or higher dose than intended. That is a dose lower or higher than 20 % of the intended dose; however, the administered dose must deviate from the intended dose to an extent where clinical consequences for the trial subject were likely to happen as judged by the investigator, although they did not necessarily occur.

Medication errors must be reported on an AE form and a specific event form, see section [8.5.1.1](#).

12.1.5 Adverse events requiring additional data collection

AEs requiring additional data collection are AEs where the additional data will benefit the evaluation of the safety of the trial product.

Some events in this trial will be adjudicated by an independent external committee as described in section [12.7.2](#).

[Table 12–1](#) lists AEs that require completion of specific event forms in the eCRFs and/or are subject to event adjudication.

Table 12–1 Adverse events requiring completion of specific event forms and/or are subject to event adjudication

Event	Specific event form	Event adjudication
Fatal event	No	Yes
Acute coronary syndrome (MI or hospitalisation for unstable angina)	Yes	Yes
Cerebrovascular event (stroke or TIA)	Yes	Yes
Heart failure (requiring hospitalisation)	Yes	Yes, all cases of heart failure requiring hospitalisation, defined as an admission to an inpatient unit or a visit to an emergency department that results in at least a 24 hour stay, will be adjudicated
Thyroid disease (including thyroid neoplasm)	Yes	Yes, (only if thyroid neoplasm or resulting in thyroidectomy)
Neoplasm (excluding thyroid neoplasm)	Yes	Yes
Renal failure	Yes	No
Pancreatitis	Yes	Yes
Medication error (see section 12.1.4)	Yes	No

For details about specific event forms, see section [8.5.1.2](#) and [Appendix C](#).

12.1.6 Technical complaints

A technical complaint is any written, electronic, or oral communication that alleges product (medicine or device) defects. The technical complaint may be associated with an AE, but does not concern the AE itself.

Examples of technical complaints:

- The physical or chemical appearance of trial products (e.g. discoloration, particles or contamination)
- All packaging material including labelling
- Problems related to devices (e.g. to the injection mechanism, dose setting mechanism, push button or interface between the pen and the needle)

12.2 Reporting of adverse events

All events meeting the definition of an AE must be collected and reported. This includes events from the first trial-related activity after the subject has signed the informed consent until the end of the post-treatment follow-up period (P33), see flowchart in section [2](#). The events must be recorded in the applicable eCRF forms in a timely manner, see timelines below, [Table 12-2](#) and [Figure 12-1](#).

During each contact with the trial site staff, the subject must be asked about AEs and technical complaints, for example by asking: "Have you experienced any problems since the last contact?"

All AEs, observed by the investigator or subject, must be reported by the investigator and evaluated.

All AEs must be recorded by the investigator on an AE form. The investigator should report the diagnosis, if available. If no diagnosis is available, the investigator should record each sign and symptom as individual AEs using separate AE forms.

For SAEs, a SIF must be completed in addition to the AE form. If several symptoms or diagnoses occur as part of the same clinical picture, one SIF can be used to describe all the SAEs.

For AEs requiring additional information, a specific event form in addition to the AE form must be completed.

For all non-serious AEs, the applicable forms should be signed when the event is resolved or at the end of the trial at the latest.

Timelines for initial reporting of AEs:

The investigator must complete the following forms in the eCRF within the specified timelines:

- **SAEs:** The AE form **within 24 hours** and the SIF **within 5 calendar days** of the investigator's first knowledge of the SAE. Both forms must be signed within 7 calendar days from the date the information was entered in the eCRF.
- **For SAEs requiring reporting on a specific event form:** In addition to the above the specific event form within **14 calendar days** from the investigator's first knowledge of the AE.
- **For non-serious AEs:** The AE form within **14 calendar days** of the investigators first knowledge of the AE.
- **For non-serious AEs requiring additional data collection:** The AE form and the specific event form within **14 calendar days** of the investigator's first knowledge of the event.
- **Events for Adjudication:** The adjudication form within **14 calendar days** of the investigator's first knowledge of the AE, see section [12.7.2](#).

Table 12–2 Summary of reporting timelines for adverse events

Event Type / Form	AE Form ¹	SIF ¹	Specific event form ¹	Adjudication form ¹
SAE	24 hours ²	5 days ²		
Non-serious AE	14 days			
Non-serious AE with additional data collection	14 days		14 days	14 days ³
SAE with additional data collection	24 hours ²	5 days ²	14 days	14 days ³

¹All days are calendar days

²Forms must be signed within 7 days

³If qualifying for adjudication

If the eCRF is unavailable, the concerned AE information must be reported on a paper AE form and sent to Novo Nordisk by fax, e-mail or courier within the same timelines as stated above. When the eCRF becomes available again, the investigator must enter the information into the eCRF.

Contact details (fax, telephone, e-mail and address) are provided in the investigator trial master file.

[figure not shown]

Figure 12–1 Reporting of adverse events

Novo Nordisk assessment of AE expectedness:

Novo Nordisk assessment of expectedness is performed according to the following reference documents:

- IDegLira; current version of the company core data sheet and any updates thereto.
- IDeg; current version of the company core data sheet and any updates thereto.

Reporting of trial product-related SUSARs by Novo Nordisk:

Novo Nordisk will notify the investigator of trial product-related suspected unexpected serious adverse reactions (SUSARs) in accordance with local requirements and ICH GCP¹. In addition, the investigator will be informed of any trial-related SAEs that may warrant a change in any trial procedure.

In accordance with regulatory requirements, Novo Nordisk will inform the regulatory authorities of trial product-related SUSARs. In addition, Novo Nordisk will inform the institutional review boards (IRBs) of trial product-related SUSARs in accordance with local requirement and ICH GCP¹, unless locally this is an obligation of the investigator.

Novo Nordisk products used as concomitant medication:

If an AE is considered to have a causal relationship with a Novo Nordisk marketed product used as concomitant medication in the trial, it is important that the suspected relationship is reported to

Novo Nordisk, e.g. in the alternative aetiology section on the SIF. Novo Nordisk may need to report this AE to relevant regulatory authorities.

12.3 Follow-up of adverse events

The investigator must record follow-up information by updating the forms in the eCRF. Follow-up information must be reported to Novo Nordisk according to the following:

- **SAEs:** All SAEs must be followed until the outcome of the event is “recovered/resolved”, “recovered/resolved with sequelae” or “fatal”, and until all queries have been resolved. Cases of chronic conditions, cancer or AEs ongoing at time of death (where death is due to another AE) may be closed with the outcome “recovering/resolving” or “not recovered/not resolved”. Cases can be closed with the outcome of “recovering/resolving” when the subject has completed the follow-up period and is expected by the investigator to recover.
The SAE follow-up information should only include new (e.g. corrections or additional) information and must be reported **within 24 hours** of the investigator’s first knowledge of the information. This is also the case for previously non-serious AEs which subsequently become SAEs.
- **Non-serious AEs:** Non-serious AEs must be followed until the outcome of the event is “recovering/resolving”, “recovered/resolved” or “recovered/resolved with sequelae” or until the end of the follow-up period stated in the protocol, whichever comes first, and until all queries related to these AEs have been resolved. Cases of chronic conditions, cancer or AEs ongoing at time of death (where death is due to another AE) may be closed with the outcome “recovering/resolving” or “not recovered/not resolved”. Cases can be closed with the outcome of “recovering/resolving” when the subject has completed the follow-up period and is expected by the investigator to recover.
- **Non-serious AE with additional data collection:** Non-serious AE with additional data collection must be followed as specified for non-serious AEs. Follow-up information on AE with additional data collection should only include new (e.g. corrections or additional) information and must be reported within 14 calendar days of the investigator’s first knowledge of the information.

The investigator must ensure that the recording of the worst case severity and seriousness of an event is kept throughout the trial. A worsening of an unresolved AE must be reported as follow-up with re-assessment of severity and/or seriousness of the event.

Queries or follow-up requests from Novo Nordisk must be responded to **within 14 calendar days** from the date of receipt of the request, unless otherwise specified in the follow-up request.

SAEs after end of trial: If the investigator becomes aware of an SAE with a suspected causal relationship to the IMP occurring to a subject after the subject has ended the trial, the investigator should report this SAE within the same timelines as for SAEs during the trial.

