8.3.3 Concomitant illness and medical history

A **concomitant illness** is any illness that is present at the start of the trial (i.e. at V1) or found as a result of a screening procedure. Concomitant illness includes any pre-planned procedures, surgery and any intermittent illness (e.g. allergies) that may not be apparent at the time of screening. T2DM and diabetes complications should not be recorded as concomitant illness.

Any change to a concomitant illness should be recorded during the trial. A clinically significant worsening of a concomitant illness must be reported as an AE.

Medical history is a medical event that the subject has experienced in the past. Only relevant medical history related to the evaluation of this trial should be reported at the investigator's discretion.

The information collected for concomitant illness and medical history should include diagnosis, date of onset and date of resolution or continuation, as applicable. It should be recorded at screening (V1) in the eCRF at the medical history/concomitant illness form.

It must be possible to verify the subject's medical history in source documents such as subject's medical record. If a subject is not from the investigators own practice; the investigator must make reasonable effort to obtain a copy of subject's medical record from relevant party e.g. primary physician. The investigator must document any attempt to obtain external medical information by noting the date(s) when information was requested and who has been contacted.

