17.4.1.2 Safety endpoints

Adverse events

AEs will be coded using the most recent version of the Medical Dictionary for Regulatory Activities.

A TEAE is defined as an event that has onset date on or after the first day of exposure to randomised treatment and no later than 7 days after the last day of randomised treatment. If the event has onset date before the first day of exposure on randomised treatment and increases in severity during the treatment period and until 7 days after the last drug date, then this event should also be considered as a TEAE. Here the first day of IMP administration is defined as the first day of exposure to randomised treatment.

TEAEs are summarised descriptively, whereas non-TEAEs are presented in listings. TEAE data will be displayed in terms of the number of subjects with at least one event (N), the percentage of subjects with at least one event (%), the number of events (E) and the event rate per 100 years of exposure (R).

Summaries of TEAEs and of serious TEAEs will be presented as an overview including all AEs, serious AEs, number of deaths, AEs by severity, AEs by relation to treatment and AEs of special interest including AEs leading to withdrawal.

Furthermore summary tables based on system organ class and preferred terms are made for:

- All TEAEs
- Serious TEAEs
- Possibly or probably related TEAEs
- Severe, moderate and mild TEAEs
- TEAEs reported by safety areas of interest
- TEAEs with preferred term that are experienced by at least 5% of the subjects in any treatment arm or by at least 5% of all subjects

A listing for non-TEAEs with onset date before the first day of exposure to randomised treatment will be presented. A listing will also be presented for non-TEAEs collected after the treatment emergent period according to the definition of TEAE.

Classification of Hypoglycaemia

Treatment emergent: hypoglycaemic episodes will be defined as treatment emergent if the onset of the episode occurs on or after the first day of trial product administration, and no later than 7 days after the last day on trial product.

Nocturnal hypoglycaemic episodes: are episodes occurring between 00:01 and 05.59 both inclusive.

[figure not shown]
Hypoglycaemic episodes are classified according to the Novo Nordisk classification of hypoglycaemia (see [Figure 17-1](#)) and the ADA classification of hypoglycaemia (see [Figure 17-2](#)).

Novo Nordisk classification of hypoglycaemia

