2.4.1.2 Safety endpoints

Adverse events

AEs will be coded using the most recent version of the Medical Dictionary for Regulatory Activities.

A TEAE is defined as an event that has onset date on or after the first day of exposure to randomised treatment and no later than 7 days after the last day of randomised treatment. If the event has onset date before the first day of exposure on randomised treatment and increases in severity during the treatment period and until 7 days after the last drug date, then this event should also be considered as a TEAE. Here the first day of IMP administration is defined as the first day of exposure to randomised treatment.

TEAEs are summarised descriptively, whereas non-TEAEs are presented in listings. TEAE data will be displayed in terms of the number of subjects with at least one event (N), the percentage of subjects with at least one event (%), the number of events (E) and the event rate per 100 years of exposure (R).

Summaries of TEAEs and of serious TEAEs will be presented as an overview including all AEs, serious AEs, number of deaths, AEs by severity, AEs by relation to treatment and AEs of special interest including AEs leading to withdrawal.

Furthermore summary tables based on system organ class and preferred terms are made for:

- All TEAEs
- Serious TEAEs
- Possibly or probably related TEAEs
- Severe, moderate and mild TEAEs
- TEAEs reported by safety areas of interest
- TEAEs with preferred term that are experienced by at least 5% of the subjects in any treatment arm or by at least 5% of all subjects

A listing for non-TEAEs with onset date before the first day of exposure to randomised treatment will be presented. A listing will also be presented for non-TEAEs collected after the treatment emergent period according to the definition of TEAE.

Hypoglycaemic events

Data on treatment emergent hypoglycaemic episodes are presented in terms of the number of subjects with at least one event (N), the percentage of subjects with at least one event (%), the number of events (E) and the event rate per 100 years (R).

Separate summaries are made for severe or BG confirmed hypoglycaemic episodes, severe or BG confirmed symptomatic hypoglycaemic episodes, , nocturnal severe or BG confirmed symptomatic hypoglycaemic episodes and the ADA classification of hypoglycaemia.

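### The treatment-emergent rule leaves out a screening-onset AE that becomes serious on treatment at an unchanged severity grade, and the data behind its severity clause are not named

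*Protocol*

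**What the plan says.** Protocol 8.5.1 and 12.2 collect AEs from the first trial activity after consent. Under Protocol 8.1.5, randomisation follows screening by at most 14 days, and the first dose is taken that day or the next.

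Protocol 12.3 sets the recording rule. "The investigator must record follow-up information by updating the forms in the eCRF", and "The investigator must ensure that the recording of the worst case severity and seriousness of an event is kept throughout the trial". On worsening it says: "A worsening of an unresolved AE must be reported as follow-up with re-assessment of severity and/or seriousness of the event". It also foresees a change of seriousness. Having set a 24-hour limit for SAE follow-up, it adds: "This is also the case for previously non-serious AEs which subsequently become SAEs".

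The TEAE definition has two limbs. The first covers onset from first exposure up to 7 days after treatment ends. The second covers earlier onset. In the SAP it begins "If the event has onset date before the first day of exposure on randomised treatment and increases in severity during the treatment period". The protocol has the same text: "increases in severity during the treatment period and until 7 days after the last drug date, then this event should also be considered" a TEAE. Neither document mentions seriousness in this limb.

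TEAEs are tabulated by arm (subjects, percentage, events, rate), with a separate table for serious TEAEs. Non-TEAEs appear in listings only, one of which is for onset before first exposure.

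Conditions already present at screening follow another route, in Protocol 8.3.3: "A clinically significant worsening of a concomitant illness must be reported as an AE".

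**The concern.** The second limb exists so that events which began before treatment and deteriorated on it are still counted. It recognises only one form of deterioration, a higher grade on the three-level severity scale. Becoming serious is another form, and for a safety table the weightier one. A screening AE that leads to hospitalisation on trial product with no change of grade would be missing from the table built to show serious events on treatment.

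There is a second, operational question. To apply the severity clause, the programmer must know whether the grade rose after the first dose. A record that keeps a pre-dose onset date and a worst grade does not show this by itself.

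At stake are the by-arm counts and rates of TEAEs and serious TEAEs in a two-arm trial that Protocol 3.2 says will support registration in Japan.

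**Working it through.** **Step 1. Are severity and seriousness distinct here?** Yes. Protocol 12.1.1 grades severity as mild, moderate or severe by interference with daily activities. Protocol 12.1.2 defines seriousness by outcomes such as death, threat to life, hospitalisation or disability. One can change without the other. Severe is also the top grade, so an AE graded severe during screening can never meet a trigger that requires an increase.

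**Step 2. Apply the written rule to an AE with onset before first exposure.**

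| Grade rises in the window | Becomes serious in the window | TEAE by rule | In serious-TEAE table |
|---|---|---|---|
| No | No | No | No |
| Yes | No | Yes | No |
| Yes | Yes | Yes | Yes |
| No | Yes | **No** | **No** |

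The first three rows behave as intended. Only the last drops out by rule, and Protocol 12.3 foresees a non-serious AE becoming serious.

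**Step 3. Compare with the concomitant-illness route.** If a pre-existing illness worsens to hospitalisation on treatment, Protocol 8.3.3 makes the worsening an AE. Its onset falls on treatment, so it meets the first limb and is a serious TEAE whatever its grade. A screening AE with the same course and an unchanged grade is a listing entry. For rises in grade, both routes lead to a TEAE.

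**Step 4. Can the severity clause be derived?** Under Protocol 12.3 a worsening goes into the existing record with the worst grade kept. No passage asks for the grade at first dose or the date of worsening. Protocol 13.1 requires an audit trail with old and new values, but its timestamp is that of data entry. Protocol 12.2 allows 14 calendar days from first knowledge to complete a non-serious AE form. A screening AE learned of at randomisation could thus be entered for the first time after dosing began, already at its worsened grade and with no earlier value in the trail. The fields of the AE form are not shown.

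**Step 5. Size.** The pre-dose window is at most 14 days, or 15 if dosing starts the day after randomisation. Treatment is 26 × 7 = 182 days, plus 7 days.

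- 14/(14 + 182 + 7) = 14/203 = 6.9% of the observed time
- 15/(15 + 182 + 7) = 15/204 = 7.4%

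The documents give no AE rate, so no event count follows from them. As an illustration only, 210 × 14/365.25 = 8.05 subject-years of screening. At an assumed 2 to 6 AEs per subject-year this gives 16 to 48 screening-onset AEs. If an assumed 5 to 10% worsen on treatment, that is 16.1 × 0.05 = 0.8 to 48.3 × 0.10 = 4.8 events. This counts events to which the severity clause would have to be applied, not events misclassified. The pool is smaller still, because 14 days is the maximum and only AEs unresolved at first dose matter. Becoming serious at an unchanged grade would be rarer again, plausibly below one event in the trial, though that too is an assumption.

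**The case against.** A reader might infer that the recording rule overwrites screening AEs, so that those which worsen on treatment vanish from the TEAE tables. The documents do not support that. Both definitions count a rise in severity, and if the event also becomes serious it is a serious TEAE. The audit trail keeps the old value. That no passage mentions a date of worsening does not prove the AE form lacks one. The SAP rule presupposes that the information can be obtained.

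A reader might also infer that any error can only conceal harm, and mainly in the IDegLira arm, because Protocol 12.6 mentions nausea, vomiting and diarrhoea when IDegLira is started. For severity this fails: if the worst grade cannot be placed in time, an AE that worsened before the first dose could equally be counted as a TEAE. For seriousness the omission does run one way, but imbalance between arms is conjecture. Under Protocol 12.2, undiagnosed symptoms each get their own form, so newly arising vomiting has an on-treatment onset of its own.

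Finally, a case that becomes serious without a change of grade is not hidden. It is reported as an SAE within 24 hours of the investigator learning of it, appears in the planned listing, and is adjudicated if of a listed type, even with onset during screening (Protocol 12.7.2).

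These objections dispose of the stronger readings. They do not remove the last row of the table in step 2, which follows from the definition itself, or supply the missing data source for the severity clause.

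**Conclusion.** The concern holds in a narrow form. By rule, an AE with onset before first exposure that becomes serious on treatment without a higher grade is outside the by-arm TEAE and serious-TEAE tables. This rests on the text alone and needs no assumption. The severity clause is a risk of misclassification in either direction, not a demonstrated loss, and it depends on an AE form that the documents do not show.

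Severity of the point: low. Probably very few events are involved, and any count rests on assumed rates. The effect is confined to descriptive safety tables, and the primary analysis is unaffected. It merits correction because it is an error in a stated rule, each missed case would be an SAE, and the change costs almost nothing.

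**What to change.** 1. In Protocol 17.4.1.2 and SAP 2.4.1.2, extend the second limb so that an AE with earlier onset is treatment emergent if its severity increases or it becomes serious in the same window.
2. In Protocol 12.3 and the eCRF instructions, for AEs with onset before the first dose and ongoing at that dose, record the date of any later increase in grade or change to serious. Use either a dated follow-up item or a new AE. If a new AE is used, the earlier record should stay at its pre-dose grade and seriousness, so that one worsening is not counted twice.
3. In the SAP, name the data items from which the second limb is derived. If the AE form already holds them, this alone settles the severity clause.
4. For records already entered, query the date of worsening for AEs that began before and were ongoing at first dose, without reference to treatment arm.

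Cost: a few words in each definition, one recording instruction and a small number of queries. TEAE counts may rise slightly. No model, sample size or clinical procedure changes.
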